9.6 Subject Disposition

Evaluable Subjects

- **Enrolled Subjects:** subjects who sign the study's informed consent form
- **Randomized Subjects:** subject who remain free from arrhythmia recurrence after signing the study ICF and are randomized into one of the study arms (OAT withdrawal or OAT).
- **Completed Subjects:** enrolled subjects who have not been discontinued, withdrawn or lost-to-follow-up from the study prior to the final (12 month) study visit.
- **Lost to Follow-up Subjects:** subjects who are enrolled and randomized, but contact is lost after most recent follow-up visit (despite 3 documented attempts to contact the subject, two (2) by documented telephone calls, and one (1) written attempt sent by registered mail).
- **Discontinued:** Subjects that have arrhythmia recurrence at any time during the Evaluation Period will be discontinued. Discontinued subjects are exited from the study prior to completion of all follow-up visits; however, they will remain in the analysis cohort until the time at which they are discontinued from the study.
- **Withdrawn Subjects:** Subjects may be withdrawn for reasons stated below in Section 9.7. Withdrawn subjects are exited from the study prior to completion of all follow-up visits; however, they will remain in the analysis cohort until the time at which they are withdrawn.

Non-Evaluable Subjects

- **Excluded:** Subjects found to not meet one of the study inclusion/exclusion criteria after the being enrolled.

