13.3 Sample Size

A total sample size of 100 (50:50) subjects will be enrolled in this pilot study. This is a pilot study and is not statistically powered to make a statistical inference.

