13.4 Analysis Population

The study contains two treatment arms with subjects either discontinuing OAT or continuing OAT. The primary analysis will be based on the intent-to-treat principle where subjects will be analyzed by the group to which they are randomized, regardless of actual treatment received. Lost-to-follow-up, discontinued, and withdrawn / early termination subjects will also be included in this analysis.

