13.7 Endpoint Analyses

13.7.1 Primary Endpoint Analysis

The primary endpoint is the occurrence of any thromboembolic event or major hemorrhagic complications during the 12-month Evaluation Period.

The Kaplan-Meier method will be used to model the time to the first occurrence of any thromboembolic event or major hemorrhagic complications during the 12-month Evaluation Period following randomization. The survival probabilities of the occurrence of any thromboembolic event or major hemorrhagic complications at the 12 month follow-up along with the corresponding 95% confidence intervals will also be presented. The equality of the survival curves between two randomization groups will be tested by the Log-rank test.

This analysis will include all subjects in the analysis population and account for censored observations. Subjects lost to follow-up, withdrew or discontinued prior to reaching their primary endpoint will be censored at their last visit.

Descriptive statistics such as 25th percentile, median and 75th percentile of time to the first occurrence as well as the 95% confidence intervals around the median time will be presented overall and by randomization groups.

The number and proportion of subjects experiencing occurrence of any thromboembolic event or major hemorrhagic complications will be summarized overall and by two randomization groups at 12 month follow up. The Fisher exact test will be used to compare the proportions between the two randomization groups.

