13.7.2 Analysis of Secondary Endpoints

Descriptive statistics including frequency and percentage for categorical secondary endpoints will be presented. The categorical secondary endpoints include minor hemorrhagic events (minor bleeds), hospitalization with any thromboembolic or major hemorrhagic event, all cause mortality, AF recurrence and repeat ablation procedures for AF.

The 95% confidence intervals for binary outcome will be computed using exact binomial method. Descriptive statistics and 95% confidence intervals will be presented overall and by randomization groups. The proportion of the occurrence will be compared between randomization groups using the Fisher exact test.

Descriptive statistics for continuous endpoints will include number of subjects, mean, standard deviation, median, 25th and 75th percentiles, minimum and maximum. These continuous secondary endpoints include the index scores of the SF-36. Change from baseline for the index score of the SF-36 will be compared between two randomization groups using the Wilcoxon rank sum test.

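### Secondary safety endpoints (minor bleeds, hospitalization, mortality) rest only on crude proportions that take no account of protocol-mandated early exit; for the primary endpoint the same comparison stands unlabelled beside Kaplan-Meier

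*Combined protocol and SAP*

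**What the plan says.** Section 13.4 analyses subjects as randomized and adds: "Lost-to-follow-up, discontinued, and withdrawn / early termination subjects will also be included in this analysis". Section 13.3 sets the size, "A total sample size of 100 (50:50) subjects will be enrolled in this pilot study", and the status: "This is a pilot study and is not statistically powered to make a statistical inference".

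Section 13.7.1 gives the primary endpoint two treatments. The first is Kaplan-Meier with 12-month survival probabilities, 95% intervals and a log-rank test, under the rule "Subjects lost to follow-up, withdrew or discontinued prior to reaching their primary endpoint will be censored at their last visit". The second is a crude summary, "The number and proportion of subjects experiencing occurrence of any thromboembolic event or major hemorrhagic complications will be summarized overall and by two randomization groups", followed by "The Fisher exact test will be used to compare the proportions between the two randomization groups". The section does not say which is decisive. It states neither the denominator of the proportion nor a rule for subjects who leave before month 12.

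Section 13.7.2 gives minor bleeds, hospitalization and all-cause mortality percentages, a Fisher comparison and this interval: "The 95% confidence intervals for binary outcome will be computed using exact binomial method". It plans no time-to-event or person-time analysis for them.

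Early exit is part of the design. Section 9.6 says: "Subjects that have arrhythmia recurrence at any time during the Evaluation Period will be discontinued". Section 11.2.1 also ends participation for test-arm subjects who resume OAT for any reason. Section 9.6 keeps discontinued subjects in the analysis cohort only up to the point of discontinuation.

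**The concern.** A 12-month proportion estimates a 12-month risk only if each subject is observed to month 12 or to the event. Here a subject who leaves at month 2 without a bleed adds a full unit to the denominator but only two months in which a bleed could be recorded. The proportion falls below the true risk, and the exact binomial interval treats that subject as fully observed.

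The shortfall grows with the exit rate, so unequal exits distort the comparison between arms. One exit rule applies to the test arm alone, and the continuous-monitoring recommendation in 11.4.2 is addressed to the off-OAT subjects, so more test-arm exits are plausible. The distortion would then favour withdrawal, the direction the study hopes to support. In a pilot that disclaims inference, the estimates and intervals are the main product, and for the three secondary safety endpoints no other planned analysis corrects them.

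**Working it through.** **Inputs from the documents.** 50 subjects per arm (13.3); early exits kept in the analysis (13.4); mandatory exit rules (9.6, 11.2.1, 11.3). There is no power calculation and no exit rate, so there is no planned figure to reproduce.

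**Assumed inputs.** Exits by 12 months of 10%, 25%, 40% and 50%. The only loose anchor is the roughly 75% ablation success rate in 5.1, which is not a recurrence rate for this selected population. True 12-month risks of 2%, 5% and 10%, chosen with the background rates in 5.1 in view: under 2 to over 10 strokes per 100 patient-years untreated, and 1.5 to 4.2 major hemorrhages per 100 patient-years on OAT. Hazards are constant and exits are independent of risk.

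**1. Understatement.** Let L = -ln(1 - risk) and M = -ln(1 - exit). With all randomized in the denominator,

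expected crude proportion = L/(L + M) × (1 - exp(-(L + M))).

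For 5% risk and 40% exits: L = 0.0513, M = 0.5108, L + M = 0.5621, exp(-0.5621) = 0.570. The result is (0.0513/0.5621) × 0.430 = 3.92%.

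| Exits | Crude at true 5% | Crude/true, risks 2-10% |
|---|---|---|
| 10% | 4.75% | 95% |
| 25% | 4.35% | 87% |
| 40% | 3.92% | 78-79% |
| 50% | 3.62% | 72-73% |

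**2. Unequal exits.** True risk is 5% in both arms.
- Control 25%, test 40%: 4.35% against 3.92%, ratio 0.90.
- Control 10%, test 40%: 4.75% against 3.92%, ratio 0.83. In simulation at 50 per arm, the test arm shows fewer events in 48% of trials and more in 32%.
- Equal exits: ratio 1.00.

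At 10%/40% exits, a test arm with a true risk of 5.8% still has the lower mean crude proportion (4.6% against 4.75%); the two are equal at a true test risk of 6.05%. For a commoner event with 20% true risk in both arms, 40% (test) against 15% (control) exits give 15.8% against 18.5%.

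**3. The other denominator.** If only completers and subjects with events are counted, the expected value is crude/(crude + (1 - risk)(1 - exit)). At 5% risk and 40% exits this is 0.0392/(0.0392 + 0.95 × 0.60) = 6.4%; at 25% exits it is 5.75%. The bias is now upward.

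**4. Interval with no events.** The exact binomial upper limit for 0 of 50 is 1 - 0.025^(1/50) = 7.1%, whatever the follow-up. On person-time, expected person-years are 50 × exit/M and the upper rate is -ln(0.025)/person-years, which converts to a 12-month risk as 1 - exp(-rate).
- 25% exits: 43.5 person-years, rate 0.0849, risk 8.1%.
- 40% exits: 39.2 person-years, rate 0.0942, risk 9.0%.
- 50% exits: 36.1 person-years, rate 0.1023, risk 9.7%.

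With 50 full person-years the two limits agree at 7.1%, so the gap is due entirely to lost follow-up.

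**5. Test and estimator behaviour.** With equal 5% risks, Fisher rejects in 0.5-0.7% of simulated trials. Mean Kaplan-Meier estimates return to about 5.0% in both arms when exits are independent of risk.

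**The case against.** The strongest reply is that 13.7.1 already leads with Kaplan-Meier, 95% intervals and log-rank, and censors exits. That stands. A reader might infer that the primary result itself ignores censoring; the documents do not support this. What remains for the primary endpoint is a second analysis with no label and no stated denominator. The distortion there is also small: at an assumed 4% true risk and exits of 40% (test) against 15% (control), the proportions are 3.1% against 3.7%, about 0.3 of a subject per arm of 50.

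Second, the all-randomized denominator is inferred, not written. Section 13.4 makes it the likelier reading, but 9.6 limits how long discontinued subjects stay in the cohort. Counting completers plus events would turn that same 4% scenario into 5.2% (test) against 4.3% (control), making withdrawal look worse. This also stands: the direction of bias depends on a choice the plan leaves open.

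Third, not every early exit is counted as event-free. A subject with an event before exit counts as an event, and for AF recurrence or repeat ablation the exit can itself be the event.

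Fourth, the exit gap is assumed. AF recurrence ends participation in both arms, Table 3 schedules monitoring without separating the arms, and OAT resumption may often follow a recurrence that has already ended participation. More test-arm exits are plausible, but their size is unknown.

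Fifth, Kaplan-Meier is not a full remedy. Exits at AF recurrence or OAT resumption may be related to event risk. With sparse data the Greenwood variance is zero in an arm without events: in the 4% scenario, at least one arm has none in about 32% of trials (1 - (1 - 0.9686^50)(1 - 0.9631^50)). An exact method must be kept.

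**Conclusion.** The concern holds for minor bleeds, hospitalization and all-cause mortality, where 13.7.2 offers nothing that accounts for incomplete follow-up. On the all-randomized reading, 12-month risk is understated by about 5% of its value at 10% exits and by 27-28% at 50%. The interval is too optimistic when no events are seen. The withdrawal arm is favoured only if its exits are the more frequent. For the primary endpoint the point is limited to labelling and the missing denominator.

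A reader might go further and conclude that the plan will produce a false finding of safety. The figures do not support that: Fisher rejections stay under 1% when risks are equal, and 13.3 disclaims inference. The harm lies in the reported estimates, their direction and their intervals. All sizes rest on assumed exit rates, constant hazards and exits independent of risk.

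**What to change.** - **13.7.2:** make events per person-year with exact Poisson 95% intervals by arm the main estimate for minor bleeds, hospitalization and mortality. Cumulative incidence to 12 months is an alternative, with death as the competing event for the non-fatal endpoints. Show raw counts, the denominator and person-time by arm as description.
- **13.7.1:** name the 12-month Kaplan-Meier risk difference with its 95% interval as the estimate. Label the Fisher comparison as supportive and give its denominator. Where an arm has zero events, report an exact person-time limit instead of a Greenwood interval.
- **Both sections:** state that the estimates assume exits are unrelated to event risk, and that this may fail for exits at AF recurrence or OAT resumption.

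The cost is SAP wording, slightly more programming and wider intervals, which reflect the follow-up actually obtained.

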13.7.2 Analysis of Secondary Endpoints

Descriptive statistics including frequency and percentage for categorical secondary endpoints will be presented. The categorical secondary endpoints include minor hemorrhagic events (minor bleeds), hospitalization with any thromboembolic or major hemorrhagic event, all cause mortality, AF recurrence and repeat ablation procedures for AF.

The 95% confidence intervals for binary outcome will be computed using exact binomial method. Descriptive statistics and 95% confidence intervals will be presented overall and by randomization groups. The proportion of the occurrence will be compared between randomization groups using the Fisher exact test.

Descriptive statistics for continuous endpoints will include number of subjects, mean, standard deviation, median, 25th and 75th percentiles, minimum and maximum. These continuous secondary endpoints include the index scores of the SF-36. Change from baseline for the index score of the SF-36 will be compared between two randomization groups using the Wilcoxon rank sum test.

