13.6 Demographic and Baseline Characteristics

The descriptive statistics of demographic and baseline characteristics include but are not limited to (1) age; (2) gender; (3) race; (4) ethnicity; (5) medical history conditions; and (6) AF history and will be presented overall and by randomization group. The descriptive statistics including number of subjects, mean, median, 25th and 75th percentiles, minimum, maximum and standard deviation will be presented for continuous variables. Frequency and percentage will be presented for categorical variables. The Fisher exact test will be used to examine the categorical demographic and baseline characteristics between two randomization groups. Wilcoxon rank sum test will be used for the continuous variables.

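### Fisher's exact test for the categorical secondary endpoints is valid but conservative at 50 per arm; Boschloo's test keeps the 5% guarantee with somewhat more power, and 13.7.1 should name the governing primary test

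*Combined protocol and SAP*

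**What the plan says.** Section 13.7.2 covers minor bleeds, hospitalization with a thromboembolic or major hemorrhagic event, all-cause mortality, AF recurrence and repeat ablation. It asks for frequencies and percentages, and adds: "The 95% confidence intervals for binary outcome will be computed using exact binomial method". The comparison between arms is then fixed: "The proportion of the occurrence will be compared between randomization groups using the Fisher exact test". Sections 13.7.2.1 to 13.7.2.5 ask only for descriptive summaries of these endpoints.

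Section 13.7.1 compares the arms twice on the primary endpoint. After the Kaplan-Meier estimates: "The equality of the survival curves between two randomization groups will be tested by the Log-rank test". After the crude 12-month proportions: "The Fisher exact test will be used to compare the proportions between the two randomization groups". The time-to-event analysis has a censoring rule: "Subjects lost to follow-up, withdrew or discontinued prior to reaching their primary endpoint will be censored at their last visit". Neither test is called primary, supportive or descriptive.

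On size, section 13.3 states: "A total sample size of 100 (50:50) subjects will be enrolled in this pilot study". It continues: "This is a pilot study and is not statistically powered to make a statistical inference". No significance level, sidedness, power, event rate or effect size is given.

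**The concern.** Fisher's test conditions on the total number of events. With 50 per arm and few events, only a handful of splits are possible for each total, so the p-value moves in large steps and the test often cannot get close to 5%. With five events or fewer in the whole study it cannot reach 0.05 at all. Another exact test gives the same protection against false positives and rejects somewhat more often. What is at stake is a modest amount of sensitivity to a real difference between withdrawal and continuation on the secondary safety endpoints.

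A smaller matter concerns the primary endpoint. Two p-values will come from the same subjects, they can lie on either side of 0.05, and the plan does not say which one a reader should rely on.

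**Working it through.** **Inputs.** 50 per arm (section 13.3); Fisher's test for proportions (13.7.1, 13.7.2); log-rank for time to first event (13.7.1). Assumed, because the documents do not give them: a two-sided 5% level, and all event rates. The plan's 100 subjects come from no stated calculation, so there is no figure of its own to reproduce.

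**One table by hand.** At 5 v 0 events the two-sided Fisher p-value is 2 × C(50,5)/C(100,5) = 2 × 2,118,760/75,287,520 = 0.056. This is the most extreme split possible with five events. At 4 v 0 it is 0.117; at 6 v 0 it is 0.027.

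**True size.** With x and y events in the two arms, at rates p1 and p2,

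Pr(reject) = Σx Σy b(x; 50, p1) b(y; 50, p2) · 1[Fisher p(x, y) ≤ c],

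where b is the binomial probability and the sum runs over all 51 × 51 tables. Setting p1 = p2 and c = 0.05 gives Fisher's size:

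| Common rate | 2% | 5% | 10% | 20% | 30% | 50% |
|---|---|---|---|---|---|---|
| True size | 0.04% | 0.72% | 1.8% | 2.8% | 3.1% | 3.5% (maximum) |

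**Boschloo's test.** It uses the Fisher p-value as its statistic and takes the largest cutoff c whose size, maximised over the common rate, is at most 5%. At 50 per arm that is c = 0.0693, with maximum size 4.87%; the next attainable cutoff gives 5.06%. Because 0.0693 exceeds 0.05, every table that Fisher rejects is rejected here too. Boschloo's size also falls well below 5% for rare events: 2.1% at a common rate of 5%.

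**Power**, same sum with p1 ≠ p2:

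| Assumed rates | Fisher | Boschloo | Gain (points) |
|---|---|---|---|
| 2% v 10% | 19.0% | 30.4% | 11.4 |
| 5% v 15% | 24.4% | 32.1% | 7.8 |
| 5% v 20% | 50.8% | 58.3% | 7.5 |
| 10% v 30% | 64.0% | 69.6% | 5.5 |
| 20% v 40% | 51.5% | 56.5% | 5.0 |
| 4% v 8% | 4.1% | 8.2% | 4.1 |
| 1.5% v 4.2% | 0.9% | 2.9% | 2.0 |
| 2% v 4% | 0.6% | 2.0% | 1.4 |

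The pair 1.5% v 4.2% borrows the major-hemorrhage rates per 100 patient-years quoted in section 5.1, purely as an illustration. The gain is not a constant: among other pairs enumerated, 10% v 20% gives 4.8 points and 2% v 15% gives 12.1.

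**Log-rank against Fisher on the primary endpoint.** Take 5 v 0 with no censoring and single event times. The expected count in the arm with events is 50/100 + 49/99 + 48/98 + 47/97 + 46/96 = 2.448, and the variance is 1.249. So χ² = (5 − 2.448)²/1.249 = 5.21 and p = 0.022, against Fisher's 0.056. At 4 v 0 the pair is 0.042 and 0.117. In simulations of 8,000 runs per scenario at 50 per arm, the verdicts differed in about 1–4% of datasets with equal rates and in 9–21% under the alternatives tried (such as 2% v 10% and 10% v 30%).

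**The case against.** The strongest reply is that nothing here is an error. A true size below 5% is a known property of a valid exact test, false positives are controlled, and Fisher's test is a standard choice for sparse tables. It is also valid conditional on the observed event total, which Boschloo's test does not claim. All of that stands.

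Second, section 13.3 disclaims powered inference, so no target is missed and the sample size is unaffected. That also stands, and it keeps the severity low. It does not remove the point, because 13.7.2 still prescribes a test, and given a prescribed test the more powerful of two valid ones is the better choice.

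Third, the gains rest on assumed rates. At very low rates, which are plausible for mortality or event hospitalization, both tests have almost no power and the change rescues nothing. It can matter for commoner endpoints such as AF recurrence, but the documents give no rates for them. Nor does Boschloo's test account for unequal follow-up: like Fisher's, it compares crude proportions.

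A reader might infer that the log-rank and Fisher results contradict each other. The documents do not support that. One compares censored event times and the other crude proportions; they can disagree without either being wrong. Section 13.7.1 presents the log-rank analysis first, which hints at its role, but does not say so.

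A reader might also want a permutation p-value for the log-rank test. Without censoring it equals Fisher's at 5 v 0 (0.056) and 4 v 0 (0.117), so it gains nothing there, and it needs care if censoring differs by arm.

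**Conclusion.** The point holds as a low-severity improvement. At 50 per arm and an assumed two-sided 5% level, Fisher's true size runs from near zero for very rare events to at most 3.5%. Boschloo's test keeps the 5% ceiling and gains about 5 to 11 points of power for differences of 8 to 20 points, and 1 to 2 points for very rare events. These figures are conditional on assumed event rates and on two arms of exactly 50; they should not be quoted as fixed properties of this trial. It would go too far to say that Fisher's test is wrong here or that the plan misses a power requirement.

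Naming the governing primary test is a separate, minor clarification. It is worth making because the two p-values can fall on opposite sides of 0.05.

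**What to change.** - **13.7.2:** replace Fisher's exact test with Boschloo's two-sided unconditional exact test for the categorical secondary endpoints, and state the significance level. Keep the planned descriptive summaries and exact confidence intervals.
- **13.7.1:** state that the log-rank test, which accounts for censoring, is the primary comparison, and that the test of crude 12-month proportions is descriptive.
- In both places, repeat that the study is a pilot with no power target, so that the p-values are read accordingly.

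The cost is a few sentences of SAP wording and standard software, with no added subjects or data. The downside is a test that fewer readers know.

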The SF-36 Questionnaire must be completed by the subjects prior to randomization and at specified follow-up visits according to Table 3.

Adverse Events (AEs)

Any untoward medical occurrence in a subject whether or not there is a relationship between the AE and the drug therapy administered will be documented and reported to the Sponsor as outlined in the Adverse Events Reporting Section (12.0) of this protocol.

Medication

All concomitant medication will be documented in the subject's chart and reported on the appropriate electronic case report form(s) (eCRF[s]). Any new medications or changes to existing medication will also be captured in the eCRFs. In case an AE is related to intake of drugs, details must be provided on the appropriate eCRF(s), including the AE form.

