13.7.2.6 Quality of Life

SF-36

Quality of life (SF-36®) at 3 and 12months after randomization will be compared to baseline. Change from baseline in physical component summary (PCS) and mental component summary (MCS) will be calculated and tested.

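### The SF-36 comparison is an unadjusted rank test on change with no between-arm estimate or interval, and at month 12 it can use only subjects still in the study

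*Combined protocol and SAP*

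**What the plan says.** All references are to the combined protocol and SAP.

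- **Test.** Section 13.7.2: "Change from baseline for the index score of the SF-36 will be compared between two randomization groups using the Wilcoxon rank sum test". Section 13.7.2.6 names the two scores: "Change from baseline in physical component summary (PCS) and mental component summary (MCS) will be calculated and tested". No covariate is mentioned, although section 9.5 stratifies randomization by gender and region.
- **Summaries.** Section 13.7.2: "Descriptive statistics for continuous endpoints will include number of subjects, mean, standard deviation, median, 25th and 75th percentiles, minimum and maximum". The intervals in that section belong to the categorical endpoints: "The 95% confidence intervals for binary outcome will be computed using exact binomial method".
- **Timing.** Section 13.7.2.6: "Quality of life (SF-36®) at 3 and 12months after randomization will be compared to baseline". Section 11.4.2: "The SF-36 Questionnaire must be completed by the subjects prior to randomization and at specified follow-up visits according to Table 3". Table 3 ticks QoL at baseline, month 3 and month 12. It has none at month 6 or at unscheduled visits, and no exit assessment.
- **Exit.** Section 9.6: "Subjects that have arrhythmia recurrence at any time during the Evaluation Period will be discontinued", and "Discontinued subjects are exited from the study prior to completion of all follow-up visits". Sections 11.3 and 11.4.3 repeat the recurrence rule for both arms. Section 11.2.1 adds that a test-arm subject who resumes OAT, for whatever reason, is also discontinued.
- **Missing scores.** No method is given for missing SF-36 data. The intent-to-treat statement in section 13.4 is about the primary analysis.

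**The concern.** Quality of life is the only potential benefit that section 5.3 names for subjects in the withdrawal arm, so the SF-36 comparison is where that benefit would show. Two separate weaknesses affect it.

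The first is precision and reporting. A rank test on change yields a p-value. A pilot that disclaims inference is most useful for its estimates and their uncertainty, yet no between-arm SF-36 difference or interval is specified. The baseline score is used only by subtraction, which is less efficient than using it as a covariate.

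The second is who contributes at month 12. Exit depends on AF recurrence, which may itself be related to quality of life, and one exit rule applies to the test arm alone. If exit differs by arm, those who remain are no longer the groups that were randomized.

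**Working it through.** **Figure to reproduce.** There is none. Section 13.3 sets 100 subjects (50 + 50) with no alpha, power, effect size, SD or dropout rate. The documents also give no SF-36 SD or correlation.

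**Step 1: precision.** Let rho be the correlation between baseline and follow-up scores, with equal variances. The variance of the between-arm difference is proportional to 2(1 − rho) for change scores and to 1 − rho² for ANCOVA on baseline. The ratio is (1 − rho²) / [2(1 − rho)] = (1 + rho)/2.

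The power columns below assume 50 per arm, two-sided 5%, a true difference of 0.5 SD and normal scores. The Wilcoxon test is taken at its asymptotic relative efficiency of 3/pi = 0.955.

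| Assumed rho | Variance ratio | Saving | Power, Wilcoxon on change | Power, ANCOVA |
|---|---|---|---|---|
| 0.3 | 0.65 | 35% | 54% | 75% |
| 0.5 | 0.75 | 25% | 69% | 82% |
| 0.7 | 0.85 | 15% | 88% | 94% |
| 0.8 | 0.90 | 10% | 97% | 99% |

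The rho = 0.5 row in full, in SD units:

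- The SD of change is √[2(1 − 0.5)] = 1. The effective Wilcoxon sample is 50 × 0.955 = 47.7 per arm, so the standard error is √(2/47.7) = 0.205. Then 0.5/0.205 − 1.96 = 0.48, which gives 69%.
- For ANCOVA the standard error is √0.75 × √(2/50) = 0.173. Then 0.5/0.173 − 1.96 = 0.93, which gives 82%.
- The difference detectable with 80% power falls from 0.57 SD to 0.49 SD.

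A simulation of 4,000 trials per setting, adjusting for baseline only, gave Wilcoxon against ANCOVA power of 53% and 73% (rho 0.3), 68% and 82% (0.5), and 88% and 94% (0.7). Type I error was 4.6% to 5.4% for both methods, so with complete data the planned test is valid.

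**Step 2: who contributes at month 12.** The exit rules stop later visits and Table 3 has no SF-36 at exit. A subject who exits before month 3 therefore has no follow-up score. One who exits between months 3 and 12 has only the month-3 score. If, as an assumption, 20% exit, 50 × 0.8 = 40 per arm remain. At rho 0.5 the power is then 59% against 73%.

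**Step 3: possible bias.** Let q be the share exiting in an arm, and let exiting subjects' mean change be D points worse than that of those who remain. The mean among those who remain then overstates the mean of all randomized by q × D. With D the same in both arms, the between-arm difference shifts by (q_test − q_control) × D, in favour of the arm with more exits.

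- Equal exit (20% and 20%), D = 10: shift 0, though each arm's mean is overstated by 0.20 × 10 = 2.0 points.
- 20% and 10%, D = 5: 0.10 × 5 = 0.5 points.
- 30% and 15%, D = 10: 0.15 × 10 = 1.5 points.

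The values of q and D are illustrative. Exit could plausibly differ by arm for two reasons in the text: the OAT-resumption rule applies to the test arm only, and the follow-up monitoring paragraph in section 11.4.2 is addressed to the off-OAT subjects, so recurrence may be found more often there.

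**The case against.** The strongest reply is about weight. Section 13.3 says the study is not powered for inference, section 10.2 lists the SF-36 among additional endpoints, and the planned test holds its type I error. On that view, preferring ANCOVA to a rank test is largely a matter of taste. The weight argument stands and lowers the severity. It does not remove the point: adjusting for a score already collected costs almost nothing, and an estimate with its interval is what a pilot can usefully deliver.

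Four stronger readings are tempting, and the documents do not support them.

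- A reader might infer that the baseline score is wasted. It enters through the change score, and at rho 0.8 the loss is only 10% of variance.
- A reader might infer that no effect size could be had at all. Means and SDs are planned, so if they are tabulated by arm a crude difference can be derived; it is simply not specified.
- A reader might infer that the SAP prescribes a completers-only analysis. Sections 13.7.2 and 13.7.2.6 do not say so. The restriction follows from the exit rules and the assessment schedule, and it applies to month 12. Subjects who exit after month 3 still contribute to the month-3 comparison.
- A reader might take the success rate of about 75% in section 5.1 to mean that a quarter will exit. That figure describes ablation studies against antiarrhythmic drugs. Here, section 9.1 admits patients already recurrence-free 3 to 21 months after ablation, so it does not transfer.

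It is also fair to say that informative exit comes from the discontinuation rules, not from the Wilcoxon test. Changing the test alone would not cure it.

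**Conclusion.** The point holds as two linked weaknesses of minor to moderate severity.

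First, the planned SF-36 analysis is valid with complete data but gives up precision and specifies no between-arm estimate or interval. The loss against ANCOVA is 10% to 35% of variance for rho from 0.8 down to 0.3, plus about 4.5% efficiency for the rank test under normality. The variance ratio rests on an assumed correlation and equal variances. The power figures also rest on normal scores and a 0.5 SD difference.

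Second, the month-12 comparison is in practice conditional on remaining in the study. Whether this biases the between-arm difference depends on whether exit, or the outcome of those who exit, differs by arm, and the documents do not allow either to be estimated. The 0.5 to 1.5 points show scale only and are not a prediction.

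**What to change.** **Analysis (sections 13.7.2 and 13.7.2.6).** Make the main SF-36 analysis an ANCOVA of PCS and MCS at months 3 and 12 adjusted for baseline score, gender and region. Alternatively, use a repeated-measures mixed model with arm, visit, arm-by-visit, baseline score, gender and region. Report the adjusted mean difference with its 95% CI for each score. Keep the Wilcoxon test on change as a sensitivity analysis.

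**Reporting.** Give the number contributing at each visit by arm, and describe the month-12 result as conditional on remaining in the study.

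**Collection.** Where feasible, obtain the SF-36 when the Final Status Form mentioned in section 11.4.3 is completed, and use it in a missing-data sensitivity analysis. This matters because the model alone cannot recover subjects who exit before month 3, and a score not taken at exit cannot be obtained later.

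**Cost.** SAP wording, plus one questionnaire and a small change to Table 3 by amendment under section 14.5. The model relies on approximate normality of the summary scores. The Wilcoxon analysis guards against failure of that assumption, but not against informative exit.
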